9.3. Serious Adverse Events

A serious adverse event (SAE) is defined as an adverse event that meets any of the following criteria:

- Results in death.
- Is life threatening; that is, poses an immediate risk of death as the event occurred.
 - This serious criterion applies even if the participant, in the view of the Investigator or Sponsor, is at immediate risk of death from the AE as it occurs. It does not apply if an AE hypothetically might have caused death if it were more severe.
- Requires inpatient hospitalization or prolongation of existing hospitalization.
 - A participant admitted to a hospital, even if he/she is released on the same day, meets the criteria for the initial inpatient hospitalization. An emergency room visit that results in admission to the hospital would also qualify for the initial inpatient hospitalization criteria. However, emergency room visits that do not result in admission to the hospital would not qualify for this criteria and, instead, should be evaluated for 1 of the other criteria in the definition of serious (e.g., life threatening adverse experience, important medical event).

- Hospitalizations for reasons not associated with the occurrence of an AE (e.g., preplanned surgery or elective surgery for a pre-existing condition that has not worsened or manifested in an unusual or uncharacteristic manner) do not qualify for reporting.
 - For example, if a participant has a condition recorded on his/her medical history and later has a preplanned surgery for this condition, it is not appropriate to record the surgery or hospitalization as an SAE, since there is no AE upon which to assess the serious criteria.
 - Please note that, if the pre-existing condition has worsened or manifested in an unusual or uncharacteristic manner, this would then qualify as an AE and, if necessary, the seriousness of the event would need to be determined.
- Results in persistent or significant disability or incapacity.
 - This serious criterion applies if the “disability” caused by the reported AE results in a substantial disruption of the participant’s ability to carry out normal life functions.
- Results in a congenital anomaly or birth defect in the offspring of the participant (whether the participant is male or female).

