9.4.1. Assessment of AEs

Adverse events will be solicited in a consistent manner at every study visit. Participants will be asked uniform open-ended questions to elicit any medically related changes in their well-being. They will also be asked if they have been hospitalized, had any accidents, used any new medications, changed concomitant medication regimens (prescription or OTC medications), noticed any changes in bowel habits or had unplanned visits to their general practitioner since the last visit.

In addition to participant observations, AEs identified from any study data (e.g., laboratory values, physical examination findings, ECG changes) or identified from review of other documents (e.g., participant diaries) that are relevant to participant safety will be documented on the AE page in the CRF.

If the participants reports an adverse event, the following will be recorded in the source and on the eCRF:

1. Description of the event
2. Date and time of onset and resolution (duration)
3. Record grading as per appropriate toxicity scale
4. Seriousness (does the event meet the above definition for an SAE)
5. Causality, relation to investigational product
6. Action taken regarding investigational product
7. Outcome
8. If any Concomitant Medications were given
9. Whether the AE resulted in participant withdrawal from the study
10. Investigator-specified assessment if the AE is related to a recent/current COVID infection
11. If a COVID positive PCR test received within the last 14 days

Signs or symptoms of a participant's atopic dermatitis should be recorded as AEs only if their nature changes considerably or their frequency or intensity increases in a clinically significant manner as compared to the clinical profile known to the Investigator from the participant's history.

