9.4.2. Assessment of Severity

The severity, or intensity, of an AE refers to the extent to which an AE affects the participant's daily activities or their health. The intensity of the AE will be rated in accordance with the CTCAE Version 5.0. Adverse events related to temperature and abnormal laboratory results that are not found in the CTCAE Version 5.0 will be rated in accordance with the FDA Guidance for Industry *Toxicity Grading Scale for Healthy Adult and Adolescent Volunteers Enrolled in Preventive Vaccine Clinical Trials* [[Appendix 14.5 Toxicity Grading Scale](#)].

Changes in the severity of an AE should be documented to allow an assessment of the duration of the event at each level of intensity to be performed. Adverse events characterized as intermittent do not require documentation of onset and duration of each episode.

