9.9. Study Halting Criteria

The study will be halted if any of the following occur:

- One fatal SAE considered definitely, probably, or possibly related to the investigational product.

- Two or more participants with a non-fatal SAE considered definitely, probably, or possibly related to the investigational product.
- Three or more participants with grade 3 AEs of the same type considered definitely, probably, or possibly related to the investigational product.
- Any participant develops a documented *Prevotella histicola* infection in a sterile space confirmed by clinical culture and/or qPCR.

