14.5. Toxicity Grading Scale

The following scales come from the FDA Guidance for Industry *Toxicity Grading Scale for Healthy Adult and Adolescent Volunteers Enrolled in Preventive Vaccine Clinical Trials*, September 2007.

Temperature Adverse Event Grading Scale

Vitals Signs*	Mild (Grade 1)	Moderate (Grade 2)	Severe (Grade 3)	Potentially Life Threatening (Grade 4)
Fever (°C)** (°F)**	38.0 – 38.4 100.4 – 101.1	38.5 – 38.9 101.2 – 102.0	39.0 – 40 102.1 – 104	> 40 >104

Laboratory Results Adverse Event Grading Scale

Serum *	Mild (Grade 1)	Moderate (Grade 2)	Severe (Grade 3)	Potentially Life Threatening (Grade 4)**
Sodium – Hyponatremia mEq/L	132 – 134	130 – 131	125 – 129	< 125
Sodium – Hypernatremia mEq/L	144 – 145	146 – 147	148 – 150	> 150
Potassium – Hyperkalemia mEq/L	5.1 – 5.2	5.3 – 5.4	5.5 – 5.6	> 5.6
Potassium – Hypokalemia mEq/L	3.5 – 3.6	3.3 – 3.4	3.1 – 3.2	< 3.1
Glucose – Hypoglycemia mg/dL	65 – 69	55 – 64	45 – 54	< 45
Glucose – Hyperglycemia Fasting – mg/dL Random – mg/dL	100 – 110 110 – 125	111 – 125 126 – 200	>125 >200	Insulin requirements or hyperosmolar coma
Blood Urea Nitrogen BUN mg/dL	23 – 26	27 – 31	> 31	Requires dialysis
Creatinine – mg/dL	1.5 – 1.7	1.8 – 2.0	2.1 – 2.5	> 2.5 or requires dialysis
Calcium – hypocalcemia mg/dL	8.0 – 8.4	7.5 – 7.9	7.0 – 7.4	< 7.0
Calcium – hypercalcemia mg/dL	10.5 – 11.0	11.1 – 11.5	11.6 – 12.0	> 12.0
Magnesium – hypomagnesemia mg/dL	1.3 – 1.5	1.1 – 1.2	0.9 – 1.0	< 0.9
Phosphorous – hypophosphatemia mg/dL	2.3 – 2.5	2.0 – 2.2	1.6 – 1.9	< 1.6
CPK – mg/dL	1.25 – 1.5 x ULN***	1.6 – 3.0 x ULN	3.1 – 10 x ULN	> 10 x ULN
Albumin – Hypoalbuminemia g/dL	2.8 – 3.1	2.5 – 2.7	< 2.5	--
Total Protein – Hypoproteinemia g/dL	5.5 – 6.0	5.0 – 5.4	< 5.0	--
Alkaline phosphate – increase by factor	1.1 – 2.0 x ULN	2.1 – 3.0 x ULN	3.1 – 10 x ULN	> 10 x ULN
Liver Function Tests –ALT, AST increase by factor	1.1 – 2.5 x ULN	2.6 – 5.0 x ULN	5.1 – 10 x ULN	> 10 x ULN
Bilirubin – when accompanied by any increase in Liver Function Test increase by factor	1.1 – 1.25 x ULN	1.26 – 1.5 x ULN	1.51 – 1.75 x ULN	> 1.75 x ULN
Bilirubin – when Liver Function Test is normal; increase by factor	1.1 – 1.5 x ULN	1.6 – 2.0 x ULN	2.0 – 3.0 x ULN	> 3.0 x ULN
Cholesterol	201 – 210	211 – 225	> 226	---
Pancreatic enzymes – amylase, lipase	1.1 – 1.5 x ULN	1.6 – 2.0 x ULN	2.1 – 5.0 x ULN	> 5.0 x ULN

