10.2 Adverse Events

Adverse events will be reported from the date of signed informed consent and through the Week 16 visit for participants entering the OLE study/28 days after cessation of dosing for participants who don't enter OLE. Adverse events occurring after the 28 days post-treatment would only be reported if the investigator considers it to be related to the study treatment.

Only treatment emergent AEs (TEAEs) will be included in the summaries, pre-treatment AEs will be included in the listings of all AEs.

All AEs will be coded using MedDRA. The dictionary will be updated through the life of the study with version 24.0 used initially. Severity of event will be coded using the Common Terminology Criteria for Adverse Events v5.0 (CTCAE).

An overview of TEAEs will be produced showing the number and percentage of participants with:

- Any TEAEs
- Any TEAE of CTCAE grade 2 or above
- Any TEAE of CTCAE grade 3 or above
- Any TEAE of CTCAE grade 4 or above
- Any fatal TEAE
- Any serious TEAE
- Any TEAE leading to permanent discontinuation of study drug
- Any TEAE leading to withdrawal from the study
- Any related TEAE
- Any related TEAE of CTCAE grade 2 or above
- Any related TEAE of CTCAE grade 3 or above
- Any related TEAE of CTCAE grade 4 or above
- Any related fatal TEAE
- Any related serious TEAE
- Any related TEAE leading to permanent discontinuation of study drug
- Any related TEAE leading to withdrawal from the study

Related events are those which were considered by the investigator to be possibly, probably or definitely related to study drug.

TEAEs will also be summarized by system organ class (SOC) and preferred term (PT). Summary tables will contain the number and percentage of participants and the number of events. A participant who has multiple events in the same SOC or the same preferred term will be counted only once in the participant counts but all events will be counted in the event counts. Adverse event summaries will be sorted by the internationally agreed SOC order ([Table 5](#)) and decreasing incidence of preferred term within SOC in the EDP1815 column.

Related TEAEs and TEAEs of CTCAE Grade 3 or above will also be summarized by SOC and PT in the same manner as described above.

Non-serious TEAEs will be also summarised by SOC and PT, however, PTs will be presented only in case of TEAEs reported by at least 5% of participants in any treatment group.

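### The only grade-based halting trigger names grade 3 alone, so on a literal reading non-serious events first recorded at grade 4 do not count towards an automatic halt

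*Protocol*

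**What the plan says.** Protocol Section 9.9 halts the study if any one of four things happens:

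- a single related SAE with a fatal outcome;
- related SAEs without a fatal outcome in at least two people;
- the trigger at issue here, "Three or more participants with grade 3 AEs of the same type considered definitely, probably, or possibly related to the investigational product";
- infection of a sterile site with *Prevotella histicola*, confirmed by laboratory test.

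In the first three, an event counts as related if the link is rated possible or stronger. Only the third refers to grade.

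On grading, Section 9.4.2 states: "The intensity of the AE will be rated in accordance with the CTCAE Version 5.0". The scale in Appendix 14.5 is used for temperature and laboratory AEs that CTCAE does not cover. That scale has a column for grade 3 (severe) and a further column whose heading begins "Potentially Life Threatening (Grade 4".

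Section 9.4.1 makes grade one item of the AE record ("Record grading as per appropriate toxicity scale") and seriousness the next, separate item. Section 9.3 defines seriousness by several alternative criteria. The life-threatening criterion is about actual danger when the event happens, with this limit: "It does not apply if an AE hypothetically might have caused death if it were more severe". Another criterion covers important medical events, by medical judgment.

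**The concern.** A halting rule should not become harder to trigger as the same toxicity gets more severe. The participant counts in Section 9.9 are open-ended upwards, but the grade is a single value. A person applying the text as written would count a grade 3 event and could leave out a grade 4 event of the same kind. Another person might assume that higher grades were meant. Identical data could then lead to a halt or to no halt, depending on who reads the rule.

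This matters because Section 9.9 is the only prespecified, event-triggered halting rule in the protocol. It covers all four cohorts, about 405 randomized participants, of whom 295 are to receive EDP1815.

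**Working it through.** The protocol gives no figure to reproduce here. The check is whether the problem case can exist, and what Section 9.9 then returns.

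**Step 1. Can an event be grade 4 and not serious?** Yes. Grade and seriousness are recorded separately (Protocol 9.4.1). Appendix 14.5 describes grade 4 as potential danger to life, whereas Section 9.3 asks for actual danger and excludes the hypothetical kind. SAP Section 10.2 also tabulates grade 4 or above and serious events on separate lines.

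**Step 2. Does any text extend the trigger beyond grade 3?** None was found in the protocol or SAP. Where the SAP includes higher grades it says so, as in "Any related TEAE of CTCAE grade 3 or above".

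**Step 3. Apply the four triggers literally.** All events are related and of the same type, each in a different participant, with no sterile-space infection. The cells give the number of participants counted.

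| Case | Fatal SAE (needs 1) | Non-fatal SAE (needs 2) | Grade 3 (needs 3) | Automatic halt |
|---|---|---|---|---|
| A. Three at grade 3, non-serious | 0 | 0 | 3 | Yes |
| B. Three first recorded at grade 4, non-serious | 0 | 0 | 0 | No |
| C. Two at grade 3 and one first recorded at grade 4, non-serious | 0 | 0 | 2 | No |
| D. Two at grade 4, both non-fatal SAEs | 0 | 2 | 0 | Yes, by the SAE trigger |
| E. Three that began at grade 3 and worsened to grade 4, non-serious | 0 | 0 | 3 if the grade 3 record counts, 0 if only the highest grade counts | Not determined |

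The inversion lies between A and B: the milder set halts the study and the more severe set does not. C shows that a single higher-grade event is enough to keep a set below the threshold.

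**Step 4. What happens to an event that worsens?** Under Section 9.4.4.1 an increase in intensity produces a second AE record, and the earlier one is closed rather than overwritten. A participant in case E therefore still has a grade 3 AE on file. Section 9.9 does not say whether that record counts.

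**Step 5. Is a first record at grade 4 realistic?** It is possible for laboratory events. Table 4-1 schedules safety laboratory tests on Days 29, 57, 85 and 113, so the gaps are 57 − 29 = 85 − 57 = 113 − 85 = 28 days. An abnormality could pass through grade 3 between two samples without being seen. The documents give no rate for this.

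**The case against.** The case for leaving the text alone has several parts, and most of them narrow the point.

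- **Shorthand.** The authors may have meant grade 3 or higher. That is plausible, but the text does not say it, and a rule that forces a halt should not depend on inferred intent.
- **SAE trigger.** Section 9.3 is wider than danger to life. A related grade 4 event that an investigator finds clinically significant could well be judged an important medical event. It then falls under the SAE trigger, which needs only two participants and no common event type. This removes many grade 4 events from the gap, though by case-by-case judgment.
- **Laboratory findings.** Section 9.10 makes them AEs only when they are clinically significant, which thins the group further.
- **Other oversight.** The Medical Monitor reviews safety information (Section 9.4), selected data are reviewed periodically in blinded form (Section 9.8), and the sponsor may suspend the study for safety at any time (Section 10.4). These are real safeguards, but none is an automatic trigger.
- **Experience to date.** Section 1.2 reports no related SAEs, with 458 people having received EDP1815. This suggests that the rule will seldom be tested, but does not settle what it means.

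A reader might also infer three stronger things that the documents do not support:

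- **That worsening removes a participant from the count.** Section 9.4.4.1 keeps the grade 3 record, so the correct statement is that its handling is undefined.
- **That grade 4 is generally assigned on a laboratory value alone.** CTCAE is the main scale and Appendix 14.5 a fallback. Some appendix parameters, such as calcium and magnesium, are not in the Section 9.10 panel. Some grade 4 entries are defined by dialysis or hospital admission, and admission is itself an SAE criterion.
- **That the protocol and SAP give conflicting halting counts.** The rows in SAP Section 10.2 are descriptive summaries and not a halting rule.

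**Conclusion.** The point holds in a limited form. Read literally, Section 9.9 returns no automatic halt for three participants with related, non-serious, same-type events first recorded at grade 4 (count 0), or for two at grade 3 and one at grade 4 (count 2). It does return a halt for three at grade 3.

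This rests on two assumptions: that the wording is applied as written, and that the events are not judged serious under any criterion in Section 9.3. Serious grade 4 events are covered. Events that worsen from grade 3 are unclear rather than excluded. It would also be too strong to say that the study would continue regardless, because a discretionary suspension stays open.

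The number of participants affected cannot be estimated from the documents and is probably small. The point is still worth correcting, because a stated safety rule gives a perverse result when followed to the letter.

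**What to change.** Reconcile Section 9.9 with the grading scales in Section 9.4.2 and Appendix 14.5. The text should state how three kinds of event enter the halting count: events at grade 4, sets of mixed grade, and events that worsen after a grade 3 record (Section 9.4.4.1). The result should be explicit and should not be inverted with respect to severity. What the rule should be, and at what thresholds, is for the sponsor's safety team, and no rule is proposed here.

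The cost is a few words in a protocol amendment. The downside is a marginally higher chance of a halt if more events come to count.

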9.10. Laboratory Measurements

Standard laboratory analyses to understand safety and tolerability include the following measurements:

Hematology	Biochemistry	Urinalysis
Complete Blood Count with differentials:	Alanine Aminotransferase (ALT)	Bilirubin
Hemoglobin	Aspartate Aminotransferase (AST)	Blood
Hematocrit	Creatinine	Glucose
Platelet count	C-Reactive Protein (CRP)	Ketones
Red blood count (with percent reticulocytes)	Gamma-glutamyl transpeptidase (GGT)	Nitrites
Mean Corpuscular Hemoglobin (MCH)	Potassium	pH
Mean Corpuscular Hemoglobin Concentration (MCHC)	Sodium	Protein
Mean Corpuscular Volume (MCV)	Total Bilirubin	Specific Gravity
White blood cell count:	Urea	
Basophils		
Eosinophils		
Lymphocytes		
Monocytes		
Neutrophils		

A serum pregnancy test will be performed on women of childbearing potential (WOCBP) at the Screening Visit. Urine pregnancy testing will be conducted on Day 1 and then monthly thereafter.

Additional testing may be ordered if needed, to further assess an adverse event (AE), or if there is any suspicion that a subject may be pregnant, throughout the course of the study.

Only abnormal laboratory test results (hematology, clinical biochemistry, or urinalysis) or other safety assessments (e.g., ECGs, vital sign measurements), which are clinically significant in the medical and scientific judgment of the investigator, are to be recorded as AEs or SAEs.

A central laboratory (or specialized central laboratories) will be used for all laboratory analyses. Details of sample collection and handling procedures will be provided in the specific laboratory manual.

9.10.1. Review of Laboratory Measurements

The Investigator must review the laboratory reports, document this review, and record any clinically relevant changes occurring during the study. If the laboratory reports are not transferred electronically, the values must be filed with the source information (including reference ranges). In most cases, clinically significant abnormal laboratory findings are those that are not associated with the underlying disease, unless judged by the Investigator to be more severe than expected for the participant's condition.

All laboratory tests with values considered clinically significantly abnormal during participation in the study or within 30 days after the last dose of IMP should be repeated until the values return to normal or baseline value or are no longer considered clinically significant by the Investigator or Medical Monitor. If such values do not return to normal/baseline within a time judged reasonable by the Investigator, the etiology should be identified, and the Sponsor notified.

All protocol-required laboratory assessments, as defined in this section, must be conducted in accordance with the laboratory manual and the SOA. Screening laboratory results will be used to confirm eligibility at Day 1. If laboratory values from non-protocol specified laboratory assessments performed at the institution's local laboratory require a change in participant management or are considered clinically significant by the Investigator (e.g., SAE or AE or dose modification), then the results must be recorded on the Adverse Events eCRF.

9.10.2. Blood Volumes

The planned maximum amount of blood collected from each participant over the duration of the study, including any extra assessments that may be required, will not exceed 145 mL. Repeat or unscheduled samples may be taken for safety reasons or for technical issues with the samples. The planned maximum amount of blood collected from each participant at a single visit will not exceed 25 mL, and the planned maximum amount of blood collected from each participant over 30 days will not exceed 48 mL.

9.11. Biomarkers

9.11.1. Genetic Testing

Optional blood samples may be collected at Day 1 for genetic testing, such as human leukocyte antigen (HLA) typing and whole genome sequencing (WGS). The data will be used to correlate with the clinical outcomes in order to identify patient group(s) who may benefit the most from EDP1815 treatment. Only genetic variants that cause different responses to EDP1815 will be assessed. This sample will be stored for a maximum of 10 years and will be destroyed if not used within this time. This is an optional collection sample where local regulations and IRBs/IECs allow. This sample will only be collected on those participants who consent to participate in this optional blood collection for genetic testing.

9.11.2. Immune Protein Markers

Immunoglobulin E (IgE) are antibodies produced by the immune system and are often raised in patients with AD, particularly with the phenotype known as ‘extrinsic’ AD (Renert-Yuval, 2021). IgE is a recognized biomarker of disease severity in AD and is regularly measured in clinical practice. It is being measured in participants to see if treatment response can be predicted by Day 1 IgE level, and also whether IgE levels improve on treatment as a biomarker of treatment success. In addition to the IgE levels, other immune protein markers such as cytokines may be measured from this sample in order to assess the anti-inflammatory and disease-modifying effects of EDP1815. These samples will be collected at Day 1 and Week 16.

9.11.3. Transcription Analysis

RNA will be collected from whole blood samples at Day 1, Week 2, Week 16 and Week 20 to quantify inflammation markers in immune cells to assess the effect of EDP1815. These samples may be analyzed subject to the clinical data in the trial. The genes to be analyzed may include those related to host immune response as well as those related to the disease pathology.

